7.5 SECONDARY ENDPOINT(S)

[figure not shown]
7.5.1 Key secondary endpoint(s)

[figure not shown]
This section is not applicable as no key secondary endpoint has been specified in the protocol.

7.5.2 (Other) Secondary endpoint(s)

The analysis of standard PK parameters is performed according to (2) and (4) as outlined in section 7.3.5 of the CTP.

7.7 EXTENT OF EXPOSURE

Treatment exposure will be primarily summarized by the total on-treatment time and has been defined in [section 5.4](#) of this TSAP.

Treatment interruptions before permanent discontinuation will not be excluded. Summary statistics for treatment time by each dose level and the dosage of BI 836880 over time will also be provided.

7.8 SAFETY ANALYSIS

All safety analyses will be performed on the treated set.

7.8.1 Adverse events

The analyses of adverse events (AE) will be descriptive in nature. All analyses of AEs will be based on the number of patients with AEs and not on the number of AEs. Two analyses will be performed. The first analysis of safety will be performed for the first part of the trial (determination of the MTD, first cycle only, dose level = initial dose at the start of the treatment, treated set). This descriptive analysis will evaluate the MTD for the monotherapy

of BI 836880. The second analysis will be performed with respect to all cycles and will act as a support for the determination of the MTD (treated set).

For analysis of duration, severity etc. of multiple AE occurrences, data on the case report form (CRF) will be collapsed into AE episodes provided that all of the following applies:

- The same MedDRA lowest level term was reported for the occurrences.
- The occurrences were time-overlapping or time-adjacent (time-adjacency of two occurrences is given if the second occurrence started on the same day or on the day after the end of the first occurrence).
- Treatment did not change between the onset of the occurrences or treatment changed between the onsets of the occurrences, but no deterioration was observed for the later occurrence.

For further details on summarization of AE data, please refer to the guideline 'Handling and summarization of adverse event data for clinical trial reports and integrated summaries' ([5](#)).

For patients treated with the test drug, that means that all adverse events occurring between first drug infusion and 42 days after last drug infusion or death, whichever occurs first, will be assigned to the on-treatment period. All adverse events occurring before any study drug infusion will be assigned to 'screening' and all adverse events occurring after last study drug infusion + 42 days will be assigned to 'post-study' (for listings only). For details on the treatment definition, see [section 6.1](#).

An overall summary of adverse events will be presented. This summary will exclude the rows 'Severe AEs', 'Significant AEs' and 'Other significant AEs' but will include additional rows for 'AEs leading to dose reduction', 'AEs leading to death' and 'AEs by highest Common Terminology Criteria (CTC) grade'.

The frequency of patients with adverse events will be summarised by highest CTC grade (grades 1, 2, 3, 4, 5 and all grades), treatment, primary system organ class and preferred term for each of the following AE tables as well as relatedness of AEs to treatment and seriousness:

- All AEs
- Drug-related AEs
- AEs leading to dose reduction
- Drug related AE leading to dose reduction
- AEs leading to treatment discontinuation
- Drug-related AEs leading to treatment discontinuation
- Drug related AEs leading to treatment discontinuation or dose reduction
- AEs leading to death
- Serious AEs
- Drug related serious AEs
- Non-serious AE with higher than 5% occurrence rate
- DLTs

All tables will be sorted by system organ classes (SOC) according to the standard sort order specified by the European Medicines Agency (EMA). Preferred terms (PTs) will be sorted by frequency (within SOC).

The above tables will be repeated with the project defined grouping of AE terms. Details of the project defined groupings are defined in the technical TSAP. In these tables the grouped AEs will replace the original PTs for all AEs that are included within the grouped term. The grouped AE categories will then be tabulated along with all remaining MedDRA PTs, sorted by descending frequency.

A reference table presenting the entire project defined groupings and MedDRA PTs within each grouping will also be produced.

Additional AE tables will be produced for AEs of special interest (hepatic injury as defined in CTP section 5.3.8.1 and dose limiting toxicities as defined by 5.3.1), providing further details on highest CTC grade, action taken with study drug and time to first onset of AE.

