If DLTs are observed in the first two consecutive patients of a previously untested dose level, subsequent enrolment to that cohort will be stopped. The Bayesian logistic regression model will be re-run to confirm that the dose-level still fulfils the EWOC criterion. Decision will be made whether the next patients will be enrolled on the same dose level, or if they will be enrolled to a lower dose level. [Figure 3.1: 1](#) shows how the decision of dose escalation is made.

[figure not shown]

Figure 3.1: 1: Escalation Decision – Combination of clinical and statistical expertise

BI 836880 infusion will be repeated every 3 weeks. In the case the patient shows a stable disease or even a response, the administration of BI 836880 can be continued up to disease progression or until intolerable toxicity has been recorded. In specific cases an intra-patient dose escalation can be granted (see [section 4.1.3](#)).

Once a MTD has been reached it is foreseen to enroll up to 12 patients on this dose level to enlarge the group of patients treated on proposed RP2D. A minimum of 12 patients must have tumour lesions evaluable for Dynamic contrast-enhanced (DCE)-MRI to allow a better interpretation of a pharmacodynamics (vascular) effect of BI 836880. Confirmation of the RP2D will be made based on all available safety, PK and Pharmacodynamics (PD) data at all treatment cycles and all dose levels.

In case of anti-tumor activity signals in a given tumor type, DSB can take the decision for a trial expansion to recruit patients with the same tumor type with the aim to generate safety and preliminary efficacy data specific to such disease. 2-3 tumor type expansion cohorts are planned. Up to a total of 20 patients may be recruited in each tumor type expansion cohort and will be treated according to same [Flow Chart](#) as patient in previous cohorts. This is to confirm RP2D in patient with specific tumor type according to study objective and to prepare further Phase II studies. This change will be implemented with a further amendment to this protocol.

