6.2.2 Treatment period(s)

A treatment cycle is defined as 3 weeks of duration. If initiation of a subsequent cycle is delayed due to medical reasons, additional visits beyond Day 21 may be necessary and may be performed at investigator's discretion, and should be recorded in the eCRF.

Patients may continue treatment as long as they have clinical benefit (no PD, no toxicities, no new anti-cancer treatment started) and patient is willing to continue.

During cycle 1, 2 and 4 intensive PK-sampling will be conducted and patients have to be observed closely for any adverse events. Therefore patients have to come to the clinic during the first four courses every week to the clinic. Additional visits are needed at day 2 for cycles 1, 2 and 4 and at day 3 for cycle 1. In course 5 and 6 the patient is requested to come to the clinic on day 8 after administration of study drug. From cycle 7 onwards no additional visits, beside day 1 including drug administration, are requested by protocol.

For the 2 ongoing patients, minimum set of procedures is mandatory. This includes safety lab, vital signs including blood pressure, adverse events, and pregnancy test if applicable. However, other assessments as indicated in the flowchart of the protocol or single lab values can be omitted according to investigator's opinion.

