7.2 NULL AND ALTERNATIVE HYPOTHESES

No formal hypothesis testing is planned in this trial. All analyses in this trial are descriptive and exploratory by nature.

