All treated patients will be included in the safety analysis. In general, safety analyses will be descriptive in nature and will be based on BI standards. No hypothesis testing is planned.

Adverse events that start before first drug intake and deteriorate under treatment will also be considered as 'treatment-emergent'.

Laboratory data will be analysed both quantitatively as well as qualitatively. The latter will be done via comparison of laboratory data to their reference ranges. Values outside the reference range as well as values defined as clinically relevant will be highlighted in the listings. Treatment groups will be compared descriptively with regard to distribution parameters as well as with regard to frequency and percentage of patients with abnormal values or clinically relevant abnormal values.

Vital signs, physical examinations, or other safety-relevant data observed at screening, baseline, during the course of the trial and at the end-of-trial evaluation will be assessed with regard to possible changes compared to findings before start of treatment.

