7.8.2 Laboratory data

The analyses of laboratory data will be descriptive in nature and will be based on BI standards “Display and Analysis of Laboratory Data” ([7](#)). CTC grade for applicable lab parameters will be calculated according to CTCAE v4.0 ([6](#)).

Descriptive statistics of all converted laboratory values by visit will be provided including changes from baseline. Frequency tables of transitions relative to the reference range and of possible clinically significant abnormalities will be produced. For those parameters that have CTC grading possible clinically significant abnormalities are defined as those laboratory values with a CTC grade ≥ 2 that have had an increase of ≥ 1 grade from baseline. For those parameters for which no CTC grade has been defined standard BI project definitions will be used to decide on clinical significance. Further frequency table will show the transition of CTC grade from baseline to worst value and last value on treatment.

Summaries will be produced of laboratory data recorded prior to treatment, on-treatment and post-treatment. For details on the treatment definition, see [section 6.1](#).

The focus of the laboratory data analysis will be on the following laboratory parameters:

[figure not shown]
- Low values: Activated Partial Thromboplastin Time (aPTT), Prothrombin Time (PT), International Normalised Ratio (INR), White Blood Cell Count (WBC) with differential, Platelets (PLT)
- High values: Aspartate Aminotransferase (AST), Alanine Aminotransferase (ALT), bilirubin, Alkaline Phosphatase (AP), Activated Partial Thromboplastin Time (aPTT), Prothrombin Time (PT), International Normalised Ratio (INR), Protein levels in urine

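### The all-cycles adverse event tables meant to support the MTD give crude percentages of patients over unequal time on drug, with no adjustment for exposure

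*SAP*

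**What the plan says.** SAP 7.8.1 describes the all-cycles analysis this way: "The second analysis will be performed with respect to all cycles and will act as a support for the determination of the MTD". The counting unit is the patient: "All analyses of AEs will be based on the number of patients with AEs and not on the number of AEs". The tables follow the same form: "The frequency of patients with adverse events will be summarised by highest CTC grade", by treatment, system organ class and preferred term. They include drug-related events and events leading to dose reduction or discontinuation.

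SAP 6.1 runs the on-treatment period from first infusion to last administration plus 42 days. SAP 7.8.1 ends it at death if that comes sooner. Treatment has no fixed length. For patients with stable disease or response, Protocol 3.1 says that "the administration of BI 836880 can be continued up to disease progression or until intolerable toxicity has been recorded".

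The plan has four features that limit the problem:
- The MTD model uses DLTs in the first cycle only (Protocol 7.3.1, SAP 7.4).
- The first adverse event analysis covers cycle 1 only, by initial dose (SAP 7.8.1).
- Treatment time is summarised by dose level (SAP 7.7).
- Time to first onset is tabulated for adverse events of special interest, which are hepatic injury and DLTs (SAP 7.8.1).

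For adverse events in general, the SAP lists no rate per patient-time, no common window beyond cycle 1 and no time-to-event summary.

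**The concern.** The percentage of patients who ever have an event rises with time on drug, even at a constant risk per unit time. A dose level that keeps patients on treatment longer, for instance because it is more active, will look more toxic in these tables. A dose level that patients leave early will look safer.

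This matters because the later cycles are meant to inform decisions. Protocol 3.1 confirms the RP2D on safety data from all cycles and all dose levels. Protocol 5.3.2 has the DSB consider findings from later courses. Cycle 1 may also separate the doses poorly. Protocol 2.3 notes that almost all anti-Ang2 molecules failed to define an MTD. Protocol 4.1.3 expects the target trough at 360 mg only after three infusions.

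One secondary endpoint is also involved: drug-related events leading to dose reduction or discontinuation (Protocol 5.1.2, SAP 5.2.2). SAP 7.5.2 covers PK only, so this endpoint is analysed only through the crude tables of SAP 7.8.1.

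**Working it through.** The plan states no figure for these tables, so there is nothing to reproduce. What follows is an illustration.

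**Inputs from the documents.** A course is 21 days (Protocol 6.2.2). The window is first infusion to last infusion plus 42 days (SAP 6.1).

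**Assumptions, not in the documents.** The risk h of a first event is constant per 21 days. Courses are not delayed, and no window is cut short by death. The course counts below are also assumed.

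**Window.** For k courses it is 21 × (k − 1) + 42 days, which is k + 1 periods of 21 days. Two courses give 63 days and eight give 189 days.

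**Fixed course counts.** Crude percentage = 1 − (1 − h)^(k+1).

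| h per 21 days | 2 courses | 4 courses | 8 courses | 12 courses |
|---|---|---|---|---|
| 5% | 14.3% | 22.6% | 37.0% | 48.7% |
| 10% | 27.1% | 41.0% | 61.3% | 74.6% |
| 20% | 48.8% | 67.2% | 86.6% | 94.5% |

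Within a row the toxicity is identical and only time on drug differs. Across rows the ranking can reverse. A dose with h = 10% and 2 courses shows 27.1%, while a dose with half that risk and 8 courses shows 37.0%. Likewise 20% with 2 courses gives 48.8%, against 61.3% for 10% with 8 courses.

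**Variable course counts.** Let K be geometric with mean m, and let s = 1 − h. Then E[s^K] = (s/m) / (1 − (1 − 1/m)s), and the crude percentage is 1 − s × E[s^K]. The extra factor s is the additional 21 days in the window. With h = 5%:
- m = 2: E[s^K] = 0.475/0.525 = 0.9048, so 1 − 0.95 × 0.9048 = 14.0%.
- m = 6: E[s^K] = 0.1583/0.2083 = 0.760, so 1 − 0.95 × 0.760 = 27.8%.

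The ratio is 27.8/14.0 = 2.0 with no difference in toxicity.

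**Effect of using patient-time.** Expected periods at risk up to the first event or the end of the window are (1 − (1 − h)^(k+1))/h. For h = 5% this is 0.1426/0.05 = 2.85 periods with 2 courses and 0.3698/0.05 = 7.40 with 8. First events per period are then 0.1426/2.85 and 0.3698/7.40, both 5%. In the reversed example, the 10% dose gives 0.271/2.71 = 10%, and the order is right again.

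**The case against.** **The MTD does not rest on these tables.** This stands. The Bayesian model uses first-cycle DLTs in a common window, a cycle-1 adverse event analysis is planned, and "No formal hypothesis testing is planned in this trial". A reader might infer that the MTD itself is biased. The documents do not support that.

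**Exposure is visible to the reader.** Treatment time by dose would show an imbalance, but as a separate summary it does not adjust the event tables. Onset times cover only the events of special interest.

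**Cohorts are small.** Escalation cohorts may have as few as two patients (Protocol 3.1). With six patients per dose, the 14.3% and 37.0% above are 0.86 and 2.22 expected patients, a gap well within chance. This limits what any table can show, adjusted or not.

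**Visit frequency.** A reader might infer that thinning visits add to the differences between doses. Visits are weekly in courses 1-4 and on days 1 and 8 in courses 5-6, and then "From cycle 7 onwards no additional visits, beside day 1 including drug administration, are requested by protocol". But the schedule for a given course is the same at every dose, and adverse events are collected continuously to the end of the residual effect period (Protocol 5.3.9). For findings made only at visits, thinning narrows the crude gap. At an assumed 2% per sample, a 12-course patient has 1 − 0.98^22 = 35.9% with the planned visits and 1 − 0.98^36 = 51.7% if visits had stayed weekly. A 2-course patient has 11.4% either way. Nor do by-visit laboratory summaries improve with thinning, since each describes values measured at that visit.

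**Laboratory tables.** A reader might also infer that these are formally MTD support. SAP 7.8.2 never says so. Its worst-value table ("Further frequency table will show the transition of CTC grade from baseline to worst value and last value on treatment") does accumulate over unequal exposure, and Protocol 7.3.4 compares groups on "frequency and percentage of patients with abnormal values or clinically relevant abnormal values". The only link to the MTD is the two-analysis text in Protocol 7.3.4, which includes a first-cycle analysis.

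**Conclusion.** The point holds for the all-cycles adverse event tables. They are named as support for the MTD, they count patients over open-ended and possibly unequal exposure, and no adjustment is planned. The existing safeguards limit the harm but do not correct these tables. What is exposed is the supporting comparison of doses beyond cycle 1, including what it contributes to the RP2D.

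Size and direction are unknown, because the documents give no duration by dose level. The figures of 14.0% against 27.8% rest on assumed constant risk and assumed geometric course counts. They show what is possible, not what will be seen. If time on drug turns out similar across doses, the distortion is small. This is an inexpensive improvement to a descriptive analysis, not a flaw in the dose-finding method.

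**What to change.** In SAP 7.8.1, for drug-related adverse events, events of CTC grade 3 or higher, and drug-related events leading to dose reduction or discontinuation, add by dose level:

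- (a) patients with a first event per patient-time at risk, with time at risk matching the on-treatment window of SAP 6.1 and ending at the first event;
- (b) cumulative incidence by the end of courses 1, 2 and 4, with patients leaving the risk set when treatment stops and the numbers at risk shown.

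Both are needed. A rate per patient-time assumes roughly constant risk and can mislead if events cluster early. The fixed windows do not need that assumption, and they lie within the courses with weekly visits.

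Define dose level as the initial dose, and end the time at risk at an intra-patient dose escalation (allowed by Protocol 4.1.3). The SAP does not now say which dose later events belong to in the all-cycles adverse event tables. Use (a) and (b) for any comparison of doses beyond cycle 1, and keep the crude tables as descriptive.

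Optionally, add course-1 versions of the worst-grade and clinically-significant-abnormality tables in SAP 7.8.2, in line with the first-cycle analysis in Protocol 7.3.4. A crude laboratory table over courses 1-4 would not help, because it still mixes exposure. At an assumed 2% per sample, patients with 2 and 4 courses (6 and 12 visits) would show 11.4% and 21.5%.

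The cost is SAP wording and a few tables from data already collected. Estimates will be imprecise in small cohorts and later courses. Stopping treatment or escalating may itself relate to tolerability, so the results remain descriptive.

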7.8.2 Laboratory data

The analyses of laboratory data will be descriptive in nature and will be based on BI standards “Display and Analysis of Laboratory Data” ([7](#)). CTC grade for applicable lab parameters will be calculated according to CTCAE v4.0 ([6](#)).

Descriptive statistics of all converted laboratory values by visit will be provided including changes from baseline. Frequency tables of transitions relative to the reference range and of possible clinically significant abnormalities will be produced. For those parameters that have CTC grading possible clinically significant abnormalities are defined as those laboratory values with a CTC grade ≥ 2 that have had an increase of ≥ 1 grade from baseline. For those parameters for which no CTC grade has been defined standard BI project definitions will be used to decide on clinical significance. Further frequency table will show the transition of CTC grade from baseline to worst value and last value on treatment.

Summaries will be produced of laboratory data recorded prior to treatment, on-treatment and post-treatment. For details on the treatment definition, see [section 6.1](#).

The focus of the laboratory data analysis will be on the following laboratory parameters:

[figure not shown]
- Low values: Activated Partial Thromboplastin Time (aPTT), Prothrombin Time (PT), International Normalised Ratio (INR), White Blood Cell Count (WBC) with differential, Platelets (PLT)
- High values: Aspartate Aminotransferase (AST), Alanine Aminotransferase (ALT), bilirubin, Alkaline Phosphatase (AP), Activated Partial Thromboplastin Time (aPTT), Prothrombin Time (PT), International Normalised Ratio (INR), Protein levels in urine

7.8.3 Vital signs

Only descriptive statistics are planned for this section of the report. A shift table will be provided for change from baseline over the course of treatment for systolic and diastolic blood pressure.

[figure not shown]
7.8.4 ECG

ECG data will be collected as described in CTP section 5.3.6. Clinically significant findings in ECG data will be reported under “Adverse events” if applicable and will be analysed accordingly. In addition patients with notable findings in QTcF or QT interval at any time on treatment will be summarised in a descriptive manner.

10. HISTORY TABLE

Table 10: 1 History table

| Version | Date (DD-MMM-YY) | Author | Sections changed | Brief description of change |
|----------------|-----------------------------|---------------|-----------------------------|---|
| Final | 21-JUN-17 | [REDACTED] | None | This is the final TSAP without any modification |
